#### **j. Halting Rules:**

The ISM of each site, DMID, and DSMB will be provided safety data in order to advise on matters of safety, including halting the trial. The safety data will consist of immediate reactogenicity events (in the 15 minutes after vaccination), reactogenicity events recorded on the memory aid (each day for the week after vaccination), AEs, and SAEs. The data will be entered into OnCore and/or REDCap and provided to the ISM, DMID, and DSMB for review. The presentation of the data will include whether any events contributing towards a halting rule have been met. The frequency of DSMB review will be defined in the charter.

The study will be halted (for further DSMB review/recommendation) if any of the following occur and it was not the result of trauma or accident, scheduled hospitalization or surgery, and is not attributable to disease relapse, GVHD, or and infection due to the immunosuppressed state of the patient:

1. If two or more subjects have an SAE within 7 days of vaccine that is determined to be related to the study vaccine after reviewing the case by the site ISM, site PI and study PI, no new subjects will be enrolled. The SAEs will be reviewed by ISM for the relationship with the study vaccine and further discussed with DMID and the Data Safety Monitoring Board.
2. If eight or more subjects have the same Grade 3 event in any reactogenicity category (excluding grade 3 redness/induration size grade 3 fatigue or grade 3 fever) that is determined to be study vaccine related, no new subjects will be enrolled. The AEs will be reviewed by the DSMB for the relationship with the study vaccine.
3. 3 or more subjects have urticaria considered to be study vaccine-related.
4. 1 or more subjects have intramuscular injection-site ulceration, abscess, or necrosis.
5. 1 or more subjects have laryngospasm, bronchospasm or systemic anaphylaxis within 24 hours of administration of study vaccine.
6. 1 or more subjects have acute weakness of limbs or cranial nerve innervated muscles.
7. Any death occurring within the first 7 days following administration of study vaccine.

If any of the halting rules are met, the study will not proceed with the remaining enrollment or vaccinations without a review by and recommendation from the DSMB to proceed. Center for Biologics Evaluation and Research (CBER) will be notified if a stopping rule has been met at any time during the study. DMID retains the authority to suspend additional enrollment and study interventions/administration of study product during the entire trial, as applicable.

**k. Safety Oversight:**

The Vanderbilt-Ingram Cancer Center (VICC) oversees patient safety and data monitoring for its investigator-initiated and NIH- National Cancer Institute (NCI) funded clinical trials through its Data and Safety Monitoring Committee (DSMC). The Committee maintains authority to intervene in the conduct of studies as necessary to ensure clinical research performed at VICC achieves the highest quality standards.

**l. Data and Safety Monitoring Committee/Quality Assurance:**

The Vanderbilt-Ingram Cancer Center (VICC) oversees patient safety and data monitoring for clinical trials through the Data and Safety Monitoring Committee (DSMC). The committee will convene on a quarterly basis and *ad-hoc* as necessary. The DSMC provides oversight of the internal audit function. During audits the Quality Assurance (QA) auditor will review selected case histories. In addition they will conduct a regulatory and pharmacy audit as needed. The data presented to the DSMC will be blinded unless the committee requests un-blinded data. The DSMC will determine if the findings in the audit report require a response from the Principal Investigator. After reviewing submitted corrective action plans, the committee has the authority to approve the continuation of the study, increase the frequency of auditing, suspend accrual, or terminate a protocol; however, this will be in discussion with the DSMB.

This trial will be monitored continuously by the study's principal investigator and on a weekly and monthly basis by the Research Team. Quarterly safety and monitoring reports are available to the DSMC. The DSMC reviews all serious adverse events reported during the previous quarter for all clinical trials active at the VICC and makes recommendations to address concerns of patient safety.

A Quality Assurance auditor under the direction of the DSMC will audit this clinical trial quarterly for compliance with adverse event reporting, regulatory and studies requirements, and data accuracy and completion. Audit reports detailing the findings are provided to the DSMC.

Any DSMC communications regarding safety evaluations will be shared with the Chair of DSMB and the DSMB. This information will also be shared with FDA-CBER and NIH.

**m. Blinding:**

Either the vaccines will be blinded and/or an un-blinded vaccinator will be available to administer the vaccine. All study staff and subjects will be blinded to which vaccine the subject will receive, except for an un-blinded vaccinator, if applicable. This individual will not inform the study team, subjects to which vaccine they administered to the subject. The un-blinded vaccinator will not participate in any other study activities. If the study vaccine is provided in a blinded manner, then research staff will be able to administer the vaccine, and an un-blinded vaccinator will not be necessary. The pharmacy will be un-blinded and will have a record of which vaccine was given to each subject.

**n. Vaccine Labeling Plan:**

The following statement will be used: "Caution: New Drug – Limited by Federal (or United States) law to investigational use" and subjects will be informed of this during the consent process.

**17. Statistical Considerations:**

- a. Sample Size Calculations:** A target of 138 subjects will be targeted, with 69 in each group. This is based on the assumption, with 80% power, that 25-30% of the subjects in the SD group will achieve a protective titer compared to 50-60% of the HD-TIV group for at least one influenza antigen. Accounting for a 20% drop out rate, 138 subjects will be recruited.

Strain	Expected Seroprotection HD-TIV	Expected Seroprotection SD-QIV	N (HD)	N (SD)	Power	Total N with 20% drop out
Expected HD-TIV seroprotection is twice as of SD-QIV						
A	40%	20%	80	80	80%	200
A	50%	25%	55	55	80%	138
A	60%	30%	40	40	80%	100
A	70%	35%	28	28	80%	70

- b. Immunogenicity analysis:** The probability of achieving a 4-fold (or greater) rise in post-vaccination HAI titers relative to baseline, as well as the probability of a HAI titer greater than 1:40, will be estimated using a binomial model, using the full analysis set. We will calculate the Bayesian posterior distribution of the probabilities under all 4 combinations of SD- and HD-TIV crossed with a single dose and two doses. From these probabilities, odds ratios will be calculated along with 95% credible intervals. These quantities will be modeled as a logit-linear function of several covariates, including CD4+/CD8+/CD19+, and IgG/IgM levels, absolute neutrophil and lymphocyte count (or their ratio), time from post-transplant to enrollment, type of preparative regimen, donor status, and stem cell source. We will use normal priors with standard deviation of 5 for all logit-linear coefficients and the baseline mean, which are not informative when transformed to the probability scale. Scale (standard deviation) parameters will be given long-tailed half-Cauchy priors, also in the interest of being uninformative. In addition, the distributions of geometric mean HAI titers for high and SD-QIV recipients will be estimated via log-normal models, and expressed as ratios in order to evaluate the evidence for higher GMT in the HD-TIV sample, after one and two vaccines. The scale parameters for priors under the log-normal model will be increased by an order of magnitude relative to the logit-linear models to ensure that they do not influence the posterior estimates. We will compare each group to document if they meet serological criteria by WHO biological standards for influenza vaccines (>40% for seroconversion, GMT >2.5-fold increase, and >70% with ≥1:40). Subjects with missing data will be excluded from the analysis, but the sensitivity of the results to missingness will be formally analyzed by comparing posterior estimates under the range of possible outcomes for the missing individuals.
- c. Safety analysis:** For the primary analysis of the safety data, the proportion of subjects in each group (using full analysis set) experiencing at least one solicited AE will be calculated along with 95% posterior credible intervals. The difference between the rates of solicited AEs between the

groups will be estimated by calculating the posterior 95% credible interval of the difference in proportions. For continuous-valued events (e.g. size of swelling) uninformative priors will be used as described in (17.b); for discrete events, a flat beta parameter with scale=shape=1 will be used as uninformative priors. For each group and each event, solicited and unsolicited AEs will be descriptively summarized. Severities of solicited and unsolicited AEs will also be descriptively summarized for each group and each type of event. Descriptive statistics will include number experiencing event, mean and 95% posterior credible interval. Maximum size of redness and swelling may be descriptively summarized for each group and event; proportion of events lasting longer beyond Day 3 may also be descriptively summarized. Subjects with missing data will be excluded from analysis, but the sensitivity of the results to missingness will be formally analyzed by comparing posterior estimates under the range of possible outcomes for the missing individuals.

- d. Influenza-Like-Illness assessment:** The percentage of individuals in each group that test positive for influenza by PCR and the number of ILIs in each group during the influenza season will be compared.

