#### 4. Prior Experience with HD-TIV in the Immunocompromised Subjects

**a. Adult HSCT Recipients.** This single-center, randomized, double-blind, phase I safety and immunogenicity trial, conducted at Vanderbilt University Medical Center, compared HD to SD-TIV in adult allogeneic HSCT recipients, not on immunosuppressive therapy for treatment of active GVHD, and at least 6 months post-transplant. Subjects were randomized in a 2:1 fashion to receive 2010-11 or 2011-12 HD-TIV or SD-TIV. Forty-four subjects were enrolled (19 in year 1 and 25 in year 2) at a median of 7.9 months after allogeneic HSCT; median age of 50.1 years; 61% male; and 100% white. Twenty-nine subjects received HD-TIV and 15 subjects received SD-TIV. The HD-TIV group had higher median IgG levels (676 vs. 469,  $p=0.025$ ). The HD group reported more local symptoms compared to SD. No serious adverse events (SAEs) were attributed to the vaccine, and no differences in systemic reactions were noted. The HD-TIV group had a higher percentage of individuals with a HAI titer ≥1:40 to H3N2 after HD-TIV, (81% versus 36%,  $p=0.004$ ) and higher GMT [207.9 versus 30.3; 177.6 95% CI difference, (63.5 - 401.8)], with GMT ratio of 6.9. These results are published in *Biology of Blood and Marrow Transplant*.

**b. Pediatric Solid Organ Transplant (SOT) Recipients.** This multi-center, randomized, double-blind, phase I safety and immunogenicity trial, conducted at Vanderbilt University Medical Center and the Children's Hospital of Pittsburgh during the 2011-12 influenza season, compared HD to SD-TIV in pediatric SOT patients. Enrollees were 3-17 years of age and at least 6 months post-transplant. The mean age was 11.25 years, 68% were male, transplanted organs were 45% renal, 26% heart, 21% liver, 5% lung, and 5% intestinal, with median of 2.2 years since transplant. Twenty-three subjects were given HD and 15 were given SD-TIV. No individuals had rejection associated with vaccination. Fatigue and body ache were greater in the HD group compared to the SD group, but no differences in local reactions were noted. Subjects in the HD group had a higher percentage of a 4-fold rise to H3N2 compared to the SD group (56% versus 13%,  $p=0.08$ ). These results are published in *Pediatric Transplantation*.

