## 2. Primary and Secondary Study Objectives:

### a. Primary Objectives:

- i. To determine whether HD-TIV compared with SD-QIV will increase the probability of achieving a  $\geq 4$ -fold rise in HAI titers,  $\geq 1:40$  HAI titer, or higher GMT titers to influenza A antigens in adult HSCT recipients.

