### b. Secondary Objectives:

- i. To determine whether HD-TIV compared with SD-QIV will increase the probability of achieving a  $\geq 4$ -fold rise in HAI titers,  $\geq 1:40$  HAI titer, or higher GMT titers to influenza B antigens in adult HSCT recipients.
- ii. To determine the frequency and severity of solicited local injection site adverse events (e.g. pain/ tenderness, redness, and swelling/induration at injection site) with HD-TIV compared to SD-QIV in adult HSCT recipients.
- iii. To determine the frequency and severity of solicited systemic adverse events (e.g. fevers, headache, fatigue/malaise, nausea, body ache/myalgia, general activity level, and vomiting) with HD-TIV compared to SD-QIV in adult HSCT recipients.
- iv. To define the relationship between HAI titers, *in vivo* T and B cell phenotype, and *in vitro* influenza-specific T and B cell response in adult HSCT recipients receiving either HD-TIV or SD-QIV.
- v. To correlate HAI responses to MN responses.
- vi. To compare the persistent HAI and MN titers for all four antigen seven months after the last vaccine dose to assess for persistence of antibody titers.
- vii. To compare influenza detection by PCR during influenza season in adult HSCT recipients receiving either HD-TIV or SD-QIV.
- viii. To assess HAI and MN response in patients (e.g. repeaters) undergoing two-consecutive years revaccination using the same antigen dose
- ix. To correlate HAI responses to neuraminidase inhibition titers (NAI).

**3. Study Area:** The study will be conducted in the Oncology Units or Clinics, or Clinical Trial Centers at the following sites: **Table 2** includes the yearly average number of transplants per site.

Table 2. Clinical Sites	Average Number of Yearly Allogeneic Transplants
Northwestern University Feinberg School of Medicine	167
Fred Hutchinson Cancer Research Center	300
University Hospital, University of Alabama at Birmingham	90
Vanderbilt University Medical Center	108
TOTAL	665

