## 15. Laboratory Procedures:

- a. **Specimen Preparation, Handling, and Shipping:** Blood will be collected from a vein or from a central line from subjects. . Study personnel or clinical research staff or clinic nurse will collect the blood samples, label without personal identifiers, and deliver to the laboratory for preparation of serum and freezing of the sera until further testing and/or shipment to Vanderbilt University Medical Center for HAI, MN testing, B and T cell influenza-specific responses. Other clinical labs will be sent the local lab.
- b. **Hemagglutination Inhibition Assays (HAI):** Sera HAI testing will be tested at Vanderbilt University Medical Center. Sera will be initially diluted 1:10 per protocol. Pre-vaccination and post-vaccination sera will be analyzed simultaneously to minimize variability in the HAI assay. HAI titers will be determined for each influenza antigen included in QIV 2017-2018 or 2018-2019.
- c. **Microneutralization assays:** Sera will be shipped to at Vanderbilt University Medical Center for MN testing and results will be compared to HAI.
- d. **Neuraminidase inhibition titers.** Sera will be shipped to at Vanderbilt University Medical Center for NAi testing and results will be compared to HAI.
- e. **Influenza-specific B and T cell Responses and Immunophenotyping of B and T cells:** Samples will be collected at baseline, 5-10 days (optional) and 28-42 days after each vaccination and 5-9 months after second vaccination. After ficoll separation, peripheral blood mononuclear cells (PBMC) will be cryopreserved for future analysis. Each site will do this locally and the off-sites will ship to **[name]** laboratory at Vanderbilt in Nashville, TN. This will ensure all time points from each individual can be evaluated simultaneously. We propose to study B and T cell responses to vaccination with mass cytometry technology (CyTOF), and functional assays such as *in-vitro* IL-21 production in response to vaccine antigen.
- f. **Nasal swabs:** a nasal swab will be collected and shipped to Vanderbilt University Medical Center in Nashville, TN for PCR testing for influenza.

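### The binomial model for the titer threshold is worded as greater than 1:40, while the objectives and the WHO check use at least 1:40

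*Combined protocol and SAP*

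**What the plan says.** C.17.b is the only place that specifies how the titer-threshold outcome is modelled. After naming the 4-fold rise it continues: "as well as the probability of a HAI titer greater than 1:40, will be estimated using a binomial model". The threshold there is strict, and it is written in words, so it is not a symbol damaged in the PDF conversion.

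Elsewhere the threshold includes 1:40:

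- **Hypothesis 1 and Specific Aim 1 (section A):** at least 1:40.
- **Background (B.2):** a seroprotective HAI titer is defined as at least 1:40.
- **Pilot in adult HSCT recipients (B.4.a):** "a higher percentage of individuals with a HAI titer ≥1:40 to H3N2 after HD-TIV", 81% versus 36%.
- **Primary objective (C.2.a):** at least 1:40, as one of three measures. The sentence runs on "HAI titer, or higher GMT titers to influenza A antigens in adult HSCT recipients" directly after the inclusive sign.
- **Influenza B secondary objective (C.2.b.i):** at least 1:40.
- **WHO criteria, later in C.17.b:** "GMT >2.5-fold increase, and >70% with ≥1:40".

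Two further statements bear on the size of the effect. The laboratory section (C.15.b) says "Sera will be initially diluted 1:10 per protocol" but does not give the dilution step. The sample size section (C.17.a) assumes "25-30% of the subjects in the SD group will achieve a protective titer compared to 50-60% of the HD-TIV group" and attaches no numeric cut-off to the protective titer.

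**The concern.** HAI titers are read on a dilution series, so the difference between including and excluding a value on that series is not negligible. If 1:40 is a reportable value, the strict wording excludes everyone who reaches exactly 1:40. That changes the endpoint.

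The threshold outcome is one of the three measures in the primary objective, and seroprotection is the outcome on which the trial was sized. A programmer who follows C.17.b literally would report modelled rates for a higher cut-off than the objective names. The same paragraph would also yield a second, different proportion for the same arm through the WHO check. If the conflict stays open, the cut-off could be settled after titers are available.

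**Working it through.** **Inputs.** From the plan: 25% (SD) and 50% (HD) with 55 evaluable per arm, and 138 in total with 20% dropout (C.17.a table); starting dilution 1:10 (C.15.b). Assumed, because the plan does not state them: two-fold steps, two-sided alpha of 0.05, and the share of subjects at exactly 1:40.

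**Step 1: reproduce the plan's sample size.** The unpooled two-proportion formula is

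n = (1.960 + 0.842)² × [p1(1−p1) + p2(1−p2)] / (p1−p2)²

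For 50% v 25%: 7.85 × (0.25 + 0.1875) / 0.0625 = 54.9, so 55 per arm. With dropout, 110 / 0.80 = 137.5, so 138. The plan's figures reproduce and are not in dispute.

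**Step 2: what the strict wording scores.** Two-fold steps from 1:10 give 10, 20, 40, 80 and so on. No value lies between 40 and 80, so greater than 1:40 is the same as at least 1:80.

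| Observed titer | Objective, background, WHO check | C.17.b model, read literally |
|---|---|---|
| 1:20 or lower | non-responder | non-responder |
| 1:40 | responder | non-responder |
| 1:80 or higher | responder | responder |

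The strict rule can only lower a rate or leave it unchanged.

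**Step 3: possible size under log-normal titers.** Take a normal log2 titer with standard deviation s in both arms, set so that 50% (HD) and 25% (SD) reach at least 1:40. Moving the cut-off up one two-fold step adds 1/s to the normal quantile:

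- HD: 1 − Φ(0 + 1/s)
- SD: 1 − Φ(0.674 + 1/s)

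| s | SD, at least 1:80 | HD, at least 1:80 | Odds ratio | Power, 55 per arm |
|---|---|---|---|---|
| 1.5 | 9.0% | 25.2% | 3.42 | 62% |
| 2.0 | 12.0% | 30.9% | 3.27 | 68% |
| 2.5 | 14.1% | 34.5% | 3.19 | 71% |
| 3.0 | 15.7% | 36.9% | 3.15 | 72% |

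At the inclusive cut-off the odds ratio is (0.50/0.50) / (0.25/0.75) = 3.0. Power is 78% by the pooled two-proportion formula, which is also used for the table.

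**Step 4: is the direction of the power change fixed?** Two other assumptions about the subjects at exactly 1:40:

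- *The same fraction of responders in each arm (10%, 20%, 30%, 40%).* Rates become 45/22.5, 40/20, 35/17.5 and 30/15%. Power falls from 78% to 71%, 63%, 55% and 47%.
- *The same absolute share in each arm (5, 10, 15 points).* Rates become 45/20, 40/15 and 35/10%. Power rises to 81%, 85% and 89%.

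The direction is therefore not determined by anything in the documents.

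**The case against.** **Probably loose drafting.** The trial's own threshold is inclusive everywhere else, so a careful programmer might code at least 1:40 anyway. This stands as a reason not to claim that anyone will be misclassified. It does not clear the text. The same sentence marks the 4-fold rise as inclusive and leaves the titer threshold strict, so a literal reader has a reason to treat the two differently. No passage says that the strict wording means the inclusive one.

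**The inclusive proportion is still produced.** The WHO check requires each group's proportion at 1:40 or above. A reader might infer that the trial could no longer be compared with the pilot. The documents do not support that, because the WHO proportion can be set against the pilot result.

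**Only one measure is touched.** The 4-fold-rise and GMT analyses do not use this cut-off. It would be wrong to infer that the whole primary objective is compromised.

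**The link to the sample size is indirect.** C.17.a gives no number for the protective titer. The mismatch with the design rates holds only if the background definition carries over, which is likely but not stated.

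**A definite loss of power.** A reader might infer one from the lower rates. Step 4 shows that power can move either way. The plan also calls for posterior odds ratios with credible intervals and no frequentist test, so these power figures are only a guide.

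**Conclusion.** The inconsistency is real and sits in the current text: the only sentence that specifies the model for the titer threshold uses a different cut-off from the objective it serves. Applied literally, and assuming two-fold dilutions from 1:10, it would score at least 1:80 and lower the modelled rate in any arm with subjects at exactly 1:40.

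The size cannot be fixed from the documents. Under the log-normal illustration, 25% v 50% becomes about 9–16% v 25–37%. The absolute rates change a good deal, while the odds ratio, which is the planned contrast, moves only from 3.0 to about 3.2–3.4. That stability belongs to the log-normal assumption. In the equal-absolute-share scenario with 15 points, for example, the odds ratio is (0.35/0.65) / (0.10/0.90) = 4.85.

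The documents do not show that subjects at 1:40 will in fact be counted as unprotected; that follows only if the sentence is programmed as it stands. The planned 55 evaluable per arm and 138 in total need no change if the design rates refer to at least 1:40.

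**What to change.** In C.17.b, replace the strict threshold with a HAI titer of at least 1:40. In C.17.a, state that a protective titer means a HAI titer of at least 1:40. Use that single definition in every seroprotection model and table.

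The cost is a short text correction made before the models are programmed. It needs no new data and no change to the sample size or to the 4-fold-rise, GMT or WHO analyses.

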#### 4. Study Population:

1. **A target of at least 138 new subjects who received an allogeneic HSCT over two enrollment years: 2017-18 and 2018-2019. The following were the inclusion/exclusion criteria that were used:**

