## Proven clinical influenza illness is any breakthrough influenza illness confirmed by laboratory testing (ie Rapid antigen assay, PCR, virus culture, etc.)

## 5. Treatment Groups:

There will be two groups – HD-TIV versus SD-QIV. The subjects will be randomized in a 1:1 HD-TIV versus SD-QIV.

Treatment Group	Target Total N
Group 1 0.5 mL HD-TIV	69
Group 2 0.5 mL SD-QIV	69

**a. Randomization:** Subjects will be randomized 1:1 to either HD-TIV or SD-QIV. Randomization will be frequency-matched within each site to ensure balance between the groups and will be implemented using the Randomization Module within Vanderbilt's Research Electronic Data Capture (REDCap) database. The investigational pharmacy at each of the 4 institutions will distribute the assigned study vaccine. Because we are evaluating the immunogenicity of early timing of influenza vaccine post-transplant, we will limit enrollment to 42 (30%) subjects to  $\geq 12$  months post-transplant.

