### For block randomization

1. For subjects 12-23 months since transplant, we will do block randomization on the following question: "Is the subject currently being treated for GVHD with systemic steroids?" (yes/no); if yes, they will be evenly distributed for randomization.
2. For subjects 3-11 months since transplant, block randomization will be on the following question: "Is the subject currently being treated for GVHD with systemic steroids or does the subject fall into one or more the following criteria: history of campath (alemtuzumab); history of anti-thymocyte globulin (ATG); cord transplant; haploidentical transplant; or post-transplant cytoxan (cyclophosphamide)?"
3. **Repeaters will retain their randomization number given from their initial enrollment and will not be re-randomized.**

**b. Enrollment:** Subjects will be enrolled from the Oncology units or clinics or clinical research centers at each institution. The healthcare team will help identify individuals who are eligible and will ask permission to be approached about the study. The research team will inform the subjects of the study and its procedures. Consent will be given to them to review. Ample time will be given to explain the study and answer any questions prior to signing the consent.

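### The immunogenicity models do not name baseline HAI titre, site, the blocking question or season as covariates, and the GMT model names none; this costs efficiency, not validity

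*Combined protocol and SAP*

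**What the plan says.** Section C.17.b models two binary outcomes, the 4-fold rise and the 1:40 titre, as logit-linear in several covariates. Those named are CD4, CD8 and CD19, IgG and IgM, neutrophil and lymphocyte counts (or their ratio), and "time from post-transplant to enrollment, type of preparative regimen, donor status, and stem cell source". The list is introduced as inclusive, so it is open. Results are to be reported so that "odds ratios will be calculated along with 95% credible intervals". GMTs are compared by log-normal models, for which no covariate is named.

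On the design, C.5.a states: "Randomization will be frequency-matched within each site to ensure balance between the groups". Within C.5, subjects 12-23 months after transplant are blocked on one question: "Is the subject currently being treated for GVHD with systemic steroids". Those at 3-11 months are blocked on a composite that adds alemtuzumab, ATG, cord or haploidentical transplant, and post-transplant cyclophosphamide.

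C.14 (Visit 1) draws blood for HAI before vaccination, and C.15.b says: "Pre-vaccination and post-vaccination sera will be analyzed simultaneously to minimize variability in the HAI assay". New subjects enrol "over two enrollment years: 2017-18 and 2018-2019" (C.4). C.10 shows that the H3N2 strain differs between those seasons while the H1N1 strain does not.

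**The concern.** Pre-vaccination titre for the same antigen would be expected to predict post-vaccination titre strongly. A subject already at 1:40 before vaccination will usually count as a success on the 1:40 endpoint under either vaccine, and no exclusion criterion concerns baseline titre. Chance imbalance at baseline therefore passes straight into the 1:40 and GMT contrasts, and no named term removes it.

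Site and the blocking question were thought important enough to balance on, and section B.2 itself links GVHD with lower titres. When a design balances a prognostic factor and the model leaves it out, the variation it explains stays in the residual and the interval is wider than the design warrants. Season is not a randomisation factor, but response to H3N2 may differ with the strain.

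At stake are power and interval width in a trial of about 110 evaluable subjects, and the freedom that an open list leaves to choose covariates after unblinding.

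**Working it through.** **1. The plan's sample size.** C.17.a says "This is based on the assumption, with 80% power" and "25-30% of the subjects in the SD group will achieve a protective titer compared to 50-60% of the HD-TIV group". The table row giving 138 is 50% v 25%. No alpha is stated; two-sided 0.05 is assumed. With unpooled variance:

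n = (1.960 + 0.842)² × [0.50×0.50 + 0.25×0.75] / 0.25² = 7.849 × 0.4375 / 0.0625 = 54.9, so 55 per arm. Then 55/0.8 = 68.75, so 69 per arm and 138 in total.

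The figure reproduces. It assumes no covariate adjustment, so this point does not overturn it.

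**2. Chance imbalance at baseline.** Let a proportion p start at or above 1:40 (not given in the documents; 15-30% assumed). The SD of the between-arm difference is √[2p(1−p)/55]: 6.8 points at 15% and 8.7 at 30%. The planned effect is 25 points.

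**3. GMT, baseline titre alone.** With baseline-post correlation ρ (assumed), adjustment multiplies interval width by √(1−ρ²), and 110 subjects are worth 110/(1−ρ²).

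| ρ | Width ratio | Equivalent N |
|---|---|---|
| 0.3 | 0.954 | 121 |
| 0.5 | 0.866 | 147 |
| 0.7 | 0.714 | 216 |

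**4. GMT, all four items, by simulation.** There were 110 subjects in permuted blocks of 4 within site × time stratum × yes/no question. Log titre was analysed by least squares as a stand-in for the Bayesian model, with residual SD 1. Assumed effects of time stratum, blocking question and baseline titre (per SD) were 0.3, −0.3 and 0.3 (weak) or 0.8, −0.8 and 0.6 (moderate), with small site and season effects. The strong case raises time and question to ±1.5. The baseline effects imply within-stratum correlations of 0.3/√1.09 = 0.29 and 0.6/√1.36 = 0.51.

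Coverage of the 95% interval (4,000 trials each, no vaccine effect):

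| Effects | No covariates | Months since transplant only | Plus baseline, site, question, season |
|---|---|---|---|
| Weak | 95.2% | 95.2% | 95.1% |
| Moderate | 96.7% | 96.0% | 95.0% |
| Strong | 98.4% | 97.7% | 95.7% |

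The first column is nearest to the GMT model as written. Power for a vaccine effect of 0.6 in the moderate case (2,000 trials) is 67%, 69% and 84%.

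**5. Binary endpoint, by simulation.** Same design, maximum-likelihood logistic regression, 2,500 trials per case.

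| Case | Quantity | Months only | Full set |
|---|---|---|---|
| No vaccine effect | Rejection at 5% | 4.9% | 6.0% |
| Baseline log OR 1.0 per SD, vaccine log OR 1.1 | Power | 60.1% | 69.7% |
| | Mean log-OR interval width | 1.62 | 1.97 |
| | Mean estimated log OR | 0.91 | 1.22 |
| Baseline log OR 1.5 per SD, vaccine log OR 1.3 | Power | 63.0% | 77.4% |
| | Mean log-OR interval width | 1.60 | 2.17 |
| | Mean estimated log OR | 0.94 | 1.47 |

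Power rises by 9.6 and 14.4 points, yet the interval widens. The adjusted odds ratio is a different, conditional quantity that lies further from 1.

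The simulation error on a 5% rate is √(0.05×0.95/2500) = 0.44 points. So 4.9% is nominal, while 6.0% is a mild excess (about 2.3 standard errors), as sparse-data bias would produce. A small part of the power gain reflects that excess.

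**6. Room in the model.** At the planning rates, 55×0.50 + 55×0.25 = 41 successes are expected. The plan already names about eleven covariates.

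**The case against.** Several points on the other side stand.

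- The list is open, so the accurate statement is that the four items are not named. C.17.b also gives priors to scale parameters without saying what they belong to; site or season effects could be intended.
- A reader might infer that the model ignores the randomisation factors. It does not. Time since transplant, which separates the two blocking schemes, is named for the binary models. Regimen, donor status and stem cell source cover parts of the 3-11 month composite. Site and the blocking question itself remain.
- Section B.2 lists three correlates of poor response: GVHD, low CD19 count and early vaccination. The last two are named covariates.
- The point about subjects already at 1:40 applies to that endpoint only; the 4-fold rise is defined relative to baseline. The strain change affects H3N2 only among the influenza A antigens.
- A reader might also infer that the intervals are invalid. The documents do not support this. The planned binary analysis is not unadjusted, and with months since transplant alone the null rejection is nominal. For GMT the error is towards intervals that are too wide.
- Adding terms to a long list at this sample size carries its own risk, as the 6.0% shows.

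What does not fall away is that the covariates best placed to add precision are unnamed, and that nothing is named for GMT.

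**Conclusion.** The concern holds as a matter of efficiency and prespecification. Same-antigen baseline titre, site, the blocking question and season are not named for any immunogenicity model, and no covariate is named for GMT.

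For GMT, baseline titre alone would cut interval width by about 5%, 13% or 29% at correlations of 0.3, 0.5 or 0.7. Intervals that leave out the design factors are somewhat conservative, with coverage of about 95-98%. For the binary endpoints the gain is about 10-14 points of power, with no narrower odds-ratio interval. No inflation of false positives was found from leaving the items out.

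All these sizes rest on assumed correlations and effects, because the documents give none, and on frequentist stand-ins for the Bayesian models. The binary comparator carried only months since transplant. If the laboratory and transplant covariates already capture part of the same variation, the gain over the plan's full list will be smaller.

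**What to change.** Before unblinding, replace the open list in C.17.b with a short closed one that applies to both the logit and the log-normal models.

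- **Enter first:** log2 pre-vaccination HAI titre for the same antigen, randomisation stratum (time since transplant × blocking question, as randomised), site and season. As main effects these take 1 + 3 + 3 + 1 = 8 terms.
- **Laboratory covariates:** use pre-vaccination values only. These tests are repeated at later visits, and C.17.b does not say which visit supplies the covariate.
- **Shorten or shrink the rest:** with about 41 expected successes, eight terms plus treatment already leave about 41/9 = 4.6 per term. Drop the less useful covariates or shrink them with priors tighter than the stated SD of 5, and say which terms the scale parameters govern.
- **Report** standardised (marginal) probabilities or risk differences beside the conditional odds ratio, so that the result stays comparable with the rates used for the sample size.

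The cost is SAP wording and a few model terms; no new data are needed. The downsides are a conditional odds-ratio estimand, which the standardised results offset, and a sparse-data risk, which the shorter list and tighter priors are meant to contain.
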